4. ANALYSIS SETS (POPULATIONS FOR ANALYSIS)

Data for all participants will be assessed to determine if participants meet the criteria for inclusion in each analysis population prior to unblinding and releasing the database and classifications will be documented per standard operating procedures.

For purposes of analysis, the following analysis sets are defined:

Participant Analysis Set	Description	Applicable Analysis
Enrolled	All participants who sign the ICD.	Study conduct such as participant disposition
Randomized population	All participants who are assigned a randomization number in the IWRS regardless of whether or not the study intervention was administered.	Immunogenicity analysis population disposition
Safety population	All participants who receive the study intervention.	AE/SAE analysis

Participant Analysis Set	Description	Applicable Analysis
E-diary safety population	All participants who receive the study intervention with at least 1 day of e-diary data transmitted. Note: if all participants have at least 1 day of e-diary data transmitted, this will be the same as the safety population.	Local reactions and systemic events analysis
ITT immunogenicity population	All randomized participants who receive the study intervention and have at least 1 valid and determinate assay result after vaccination.	Supplementary analysis on primary/secondary immunogenicity endpoints
Evaluable immunogenicity population	All participants randomized in Substudy A who meet the following criteria: 
 • Are eligible for this substudy. • Received study intervention(s) to which they were randomized. • Had the 1-month postvaccination blood collection within 27 to 42 days after vaccination. • Had no major protocol violations from vaccination randomization through the 1-month postvaccination blood draw. • Had at least 1 valid and determinate assay result 1 month after vaccination. 	Primary analysis population for immunogenicity endpoints (primary/secondary/exploratory)

5. GENERAL METHODOLOGY AND CONVENTIONS

5.1. Hypotheses and Decision Rules

Both primary and secondary immunogenicity objectives are hypothesis testing objectives. The subsections below describe details of hypotheses to be tested for each objective.

5.1.1. Statistical Hypotheses for Combined Vaccine Coadministered With QIV

A total of 8 hypotheses will be tested for the first primary immunogenicity objective as described below for each vaccine component.

1. The null hypothesis (H_0) to assess noninferiority with respect to RSVpreF will be evaluated by the following hypothesis for both RSV A and RSV B as measured by NT:

$$H_0: \ln(\mu_1) - \ln(\mu_4) \leq \ln(0.5)$$

where $\ln(0.5)$ corresponds to a 2-fold margin for noninferiority, and $\ln(\mu_1)$ and $\ln(\mu_4)$ are the natural log of the geometric mean of NT 1 month after vaccination for Group 1 and Group 4, respectively.

2. The null hypothesis (H_0) to assess noninferiority with respect to BNT162b2 will be evaluated by the following hypothesis for both SARS-CoV-2 Omicron BA.4/BA.5 strain and reference strain as measured by NT:

$$H_0: \ln(\mu_1) - \ln(\mu_3) \leq \ln(0.5)$$

where $\ln(0.5)$ corresponds to a 2-fold margin for noninferiority, and $\ln(\mu_1)$ and $\ln(\mu_3)$ are the natural log of the geometric mean of NT 1 month after vaccination for Group 1 and Group 3, respectively.

3. The null hypothesis (H_0) to assess noninferiority with respect to QIV will be evaluated by the following hypothesis for each of the 4 strains included in QIV as measured by HAI titer:

$$H_0: \ln(\mu_1) - \ln(\mu_5) \leq \ln(0.5)$$

where $\ln(0.5)$ corresponds to a 2-fold margin for noninferiority, and $\ln(\mu_1)$ and $\ln(\mu_5)$ are the natural log of the geometric mean of HAI titers 1 month after vaccination for Group 1 and Group 5, respectively.

5.1.2. Statistical Hypotheses for Combined Vaccine Alone

A total of 4 hypotheses will be tested for the second primary immunogenicity objective as described below for each vaccine component.

1. The null hypothesis (H_0) to assess noninferiority with respect to RSVpreF will be evaluated by the following hypothesis for both RSV A and RSV B as measured by NT:

$$H_0: \ln(\mu_2) - \ln(\mu_4) \leq \ln(0.5)$$

where $\ln(0.5)$ corresponds to a 2-fold margin for noninferiority and $\ln(\mu_2)$ and $\ln(\mu_4)$ are the natural log of the geometric mean of NT 1 month after vaccination for Group 2 and Group 4, respectively.

2. The null hypothesis (H_0) to assess noninferiority with respect to BNT162b2 will be evaluated by the following hypothesis for both SARS-CoV-2 Omicron BA.4/BA.5 strain and reference strain as measured by NT:

$$H_0: \ln(\mu_2) - \ln(\mu_3) \leq \ln(0.5)$$

where $\ln(0.5)$ corresponds to a 2-fold margin for noninferiority and $\ln(\mu_2)$ and $\ln(\mu_3)$ are the natural log of the geometric mean of NT 1 month after vaccination for Group 2 and Group 3, respectively.

5.1.3. Statistical Hypotheses for Coadministration of 3 Individual Vaccines

A total of 8 hypotheses will be tested for the first of the secondary immunogenicity objectives, similar to [Section 5.1.1](#), except Group 1 will be replaced with Group 7.

[figure not shown]
5.1.4. Statistical Hypotheses for Coadministration of 2 Individual Vaccines

A total of 4 hypotheses will be tested for the second of the secondary immunogenicity objectives, similar to [Section 5.1.2](#), except Group 2 will be replaced with Group 6.

5.1.5. Multiplicity Adjustment

Type I error of 5% is equally split between the 2 primary immunogenicity objectives (2-sided 2.5% for each). The first primary immunogenicity objective will be achieved if all 8 null hypotheses are rejected. The second primary immunogenicity objective will be achieved if all 4 null hypotheses are rejected. The study is considered successful if either primary immunogenicity objective is achieved.

The secondary immunogenicity objectives will be tested sequentially after the primary objective(s) is achieved as described in the schema below.

5.2. General Methods

Unless otherwise stated, “CI” refers to a 2-sided CI in this document for 95% CI.

Descriptive statistics for binary variables are the proportion (%) and the numerator (n) and the denominator (N) used in the proportion calculation. The 95% CI for percentage, and for the difference in percentages, may also be presented, where appropriate.

Unless otherwise specified, descriptive statistics for continuous variables are n, mean, median, standard deviation, minimum, and maximum.

The subsections below describe the analysis for different types of endpoints.

5.2.1. Analyses for Binary Data

Descriptive statistics for binary variables are the proportion (%) and the numerator (n) and the denominator (N) used in the proportion calculation. The 95% CI for percentage, and for the difference in percentages, will also be presented, where applicable.

1. The 95% CI for the proportion (within study intervention group) will be constructed by the Clopper-Pearson method described by Newcombe.² The 95% CI will be presented in terms of percentage.
2. The 95% CI for the difference in the proportions (between study intervention groups) will be computed using the Miettinen and Nurminen method.³ The 95% CI will be presented in terms of percentage.

5.2.2. Analyses for Continuous Data

Unless otherwise specified, descriptive statistics for continuous variables are n, mean, median, standard deviation, minimum, and maximum.

The CI for the mean of the continuous variable will be constructed by the standard method based on the Student t distribution.

5.2.2.1. Geometric Means

Continuous immunogenicity endpoints will be logarithmically transformed for analysis. Geometric means and the associated 2-sided 95% CIs will be derived by calculating group means and CIs on the natural log scale, based on the Student t distribution, and then exponentiating the results.

5.2.2.2. Geometric Mean Fold Rises

GMFRs will be calculated as the group mean of the difference of logarithmically transformed assay results (later time point minus earlier time point) and exponentiating the mean. GMFRs are limited to participants with nonmissing values at both time points. The associated 2-sided 95% CIs will be obtained by constructing CIs using the Student t distribution for the mean difference on the logarithm scale and exponentiating the confidence limits.

5.2.2.3. Geometric Mean Ratios

The GMRs will be calculated as the mean of the difference of logarithmically transformed assay results between 2 groups and exponentiating the mean. Two-sided CIs will be obtained by calculating CIs using the Student t distribution for the mean difference of the logarithmically transformed assay results and exponentiating the confidence limits.

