10.11.11.3.2. Primary Endpoint(s)/Estimand(s) Analysis

Endpoint	Statistical Analysis Methods
Safety	
 Descriptive statistics will be provided for each reactogenicity endpoint in each vaccine group (Group 1 to Group 7 individually). Local reactions (pain at the injection site, redness, and swelling) and systemic events (fever, fatigue, headache, chills, vomiting, diarrhea, new or worsened muscle pain, and new or worsened joint pain) from Day 1 through Day 7 after vaccination will be presented by maximum severity and any severity. Descriptive summary statistics will include counts and percentages of participants with the indicated endpoint and the associated Clopper-Pearson 95% CIs (Section 9.3.1). AEs and SAEs will be categorized according to MedDRA terms. All of the AEs reported through the 1-month follow-up visit and SAEs reported throughout the study will be descriptively summarized with counts, percentages, and associated Clopper-Pearson 95% CI for each vaccine group (Section 9.3.1).
Immunogenicity	
 GMRs of RSV A and RSV B NTs (Group 1 to Group 4), GMRs of SARS-CoV-2 Omicron BA.4/BA.5–strain NTs and reference-strain NTs (Group 1 to Group 3), influenza strain-specific GMRs of HAI titers (Group 1 to Group 5) at 1 month after vaccination will be provided with 97.5% CIs (Section 9.3.1.2.3). Using a 2-fold noninferiority margin, success for the first primary immunogenicity objective will be declared if the lower bound of the 2-sided 97.5% CI for the GMR is greater than 0.5 for both RSV A and RSV B antigens, for both the Omicron BA.4/BA.5 and reference strains, and for all 4 QIV strains. GMRs of RSV A and RSV B NTs (Group 2 to Group 4) and GMRs of SARS-CoV-2 Omicron BA.4/BA.5–strain NTs and reference-strain NTs (Group 2 to Group 3) at 1 month after vaccination will be provided with 97.5% CIs (Section 9.3.1.2.3). Using a 2-fold noninferiority margin, success for the second primary immunogenicity objective will be declared if the lower bound of the 2-sided 97.5% CI for the GMR is greater than 0.5 for both RSV A and RSV B antigens and for both the Omicron BA.4/BA.5 and reference strains.

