10.11.11.3.3. Secondary Endpoint(s)/Estimand(s) Analysis

Endpoint	Statistical Analysis Methods
Secondary immunogenicity	
 • GMRs of RSV A and RSV B NTs (Group 7 to Group 4), GMRs of SARS-CoV-2 Omicron BA.4/BA.5–strain NTs and reference-strain NTs (Group 7 to Group 3), influenza strain-specific GMRs of HAI titers (Group 7 to Group 5) at 1 month after vaccination will be provided with 97.5% CIs (Section 9.3.1.2.3). Using a 2-fold noninferiority margin, success for the first of the secondary immunogenicity objectives will be declared if the lower bound of the 2-sided 97.5% CI for the GMR is greater than 0.5 for both RSV A and RSV B antigens, for both the Omicron BA.4/BA.5 and reference strains, and for all 4 QIV strains, after the first primary immunogenicity objective is achieved. • GMRs of RSV A and RSV B NTs (Group 6 to Group 4) and GMRs of SARS-CoV-2 Omicron BA.4/BA.5–strain NTs and reference-strain NTs (Group 6 to Group 3) at 1 month after vaccination will be provided with 97.5% CIs (Section 9.3.1.2.3). Using a 2-fold noninferiority margin, success for the second of the secondary immunogenicity objectives will be declared if the lower bound of the 2-sided 97.5% CI for the GMR is greater than 0.5 for both RSV A and RSV B antigens and for both the Omicron BA.4/BA.5 and reference strains, after the second primary immunogenicity objective is achieved.

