5.2.2.5. Analysis of Covariance

The ANCOVA model will use logarithmically transformed assay results 1 month after vaccination as dependent variables by controlling baseline assay results (in logarithm scale) to compare the immune response in the experimental group(s) with the reference group (individual vaccine alone). LS GMTs and LS GMRs will be calculated from the model-adjusted group means, group mean differences, and corresponding CIs on the natural log scale by exponentiating the results.

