6.1.1.1. Main Analysis

- Estimand strategy: Hypothetical approach ([Section 2.2.1.1](#)).
- Analysis set: Evaluable immunogenicity population ([Section 4](#)).
- Analysis timing: Final analysis of immunogenicity objective.
- Intercurrent events and missing data: All data collected after or at intercurrent events will not be included ([Section 2.2.1.1](#)); missing data will not be imputed ([Section 5.3.2](#)).
- Analysis methodology: GMR, defined as the ratio of all of the 8 strain/subgroup-specific serology results measured by RSV NT, SARS-CoV-2 NT, and HAI GMTs in Group 1 to that for single vaccine administered alone (eg, Groups 3, 4, and 5) at Visit A102 will be summarized along with the 97.5% CI ([Section 5.2.2.3](#)). Descriptive statistics, including sample size (n), and GMTs at Visit A102 will be presented for Group 1 as well as Groups 3, 4, and 5 ([Section 5.2.2](#)).
- RCDCs for each of the 8 strain/subgroup-specific serology results at Visit A102 measured by RSV NT, SARS-CoV-2 NT, and HAI titers will be plotted after vaccination for the applicable groups (eg, HAI titers for Group 1 vs Group 5).

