6.2. Secondary Endpoints

Analyses will be similar to the primary endpoint, except that Group 1 will be replaced with Group 7 and Group 2 will be replaced with Group 6.

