6.3.5.2. Sensitivity Analysis

RSV A NTs and RSV B NTs at Visit A102 will be summarized with n, GMTs, and 95% CIs for Groups 1, 2, 6, 7, and 4. Using Group 4 as reference, GMR will be summarized with 95% CI. Model-adjusted LS GMTs and LS GMRs (to Group 4) with associated 95% CIs will be based on data from all 5 groups using the ANCOVA model ([Section 5.2.2.5](#)).

SARS-CoV-2 strain-specific NTs at Visit A102 will be summarized with n, GMTs, and 95% CIs for Groups 1, 2, 6, 7, and 3. Using Group 3 as reference, GMR will be summarized with 95% CI. Model-adjusted LS GMTs and LS GMRs (to Group 3) with associated 95% CIs will be based on data from all 5 groups using the ANCOVA model ([Section 5.2.2.5](#)).

QIV strain-specific HAIs at Visit A102 will be summarized with n, GMTs, and 95% CIs for Groups 1, 7, and 5. Using Group 5 as reference, GMR will be summarized with 95% CI. Model-adjusted LS GMTs and LS GMRs (to Group 5) with associated 95% CIs will be based on data from all 3 groups using the ANCOVA model ([Section 5.2.2.5](#)).

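### The deciding noninferiority GMRs leave the collected baseline titre unused: a valid but less efficient choice, with a gain that depends on a correlation the documents do not give

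*SAP*

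**What the plan says.** SAP 5.2.2.3 defines the GMR interval without a covariate: "Two-sided CIs will be obtained by calculating CIs using the Student t distribution for the mean difference of the logarithmically transformed assay results". Protocol 9.3.1.2.3 gives the same method. SAP 6.1.1.1 applies it to the eight Group 1 comparisons ("at Visit A102 will be summarized along with the 97.5% CI"), and SAP 6.1.2.1 does so for the four Group 2 comparisons. SAP 6.2 extends it to the secondary objectives: "Group 1 will be replaced with Group 7 and Group 2 will be replaced with Group 6".

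Protocol 10.11.11.3.2 declares the first primary objective met if "the lower bound of the 2-sided 97.5% CI for the GMR is greater than 0.5 for both RSV A and RSV B antigens", and likewise for the other antigens. Protocol 10.11.11.3.3 uses the same bound for the secondary objectives: "success for the first of the secondary immunogenicity objectives will be declared if the lower bound of the 2-sided 97.5% CI".

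Blood is drawn before vaccination at Visit A101 (SAP 2.3), and SAP 6.3.1 summarises the titres at that visit. SAP 5.2.2.5 defines an ANCOVA of the 1-month log titre on log baseline titre. Its only planned use is SAP 6.3.5.2; for RSV, "Model-adjusted LS GMTs and LS GMRs (to Group 4) with associated 95% CIs will be based on data from all 5 groups". SARS-CoV-2 is handled in the same way, and HAI with three groups. The same section also reports the unadjusted GMRs, again with 95% CIs.

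**The concern.** Each objective needs every test to pass, 8 of 8 or 4 of 4 (SAP 5.1.5). The endpoint with the largest variance therefore carries most of the risk. In Table 5 that is Omicron BA.4/BA.5, with SD 1.5 and 93.8% power.

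If baseline titre predicts the 1-month titre, adjustment shrinks the residual variance and removes chance baseline imbalance from the deciding estimate. It needs no extra participants or samples. The plan has this model and does not use it for the decision. It also prints the adjusted result at a different confidence level from the one that decides success.

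**Working it through.** **Inputs.** From Protocol 10.11.11.5 and Table 5: 135 evaluable per group; one-sided alpha 0.0125; 2-fold margin; true GMR 1; natural-log SDs of 1.1 (RSV A, RSV B, H1N1, H3N2), 1.5 (BA.4/BA.5), 1.3 (reference strain) and 1.2 (both B strains). The correlation r is in neither document, so I assume a range of 0.1 to 0.5, common to all assays.

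**1. Reproduce the plan.** Non-central t with df = 2n − 2 = 268 and noncentrality ln 2 / (SD × √(2/n)). For BA.4/BA.5: 0.693 / (1.5 × 0.1217) = 3.80; critical value 2.254; power 93.8%, as stated. The other endpoints also match. The product over antigens is 90.3% for all 8 and 91.9% for the first 4, against 90.2% and 91.8% in Table 5. Multiplying the rounded single powers printed in Table 5 gives exactly 90.2% and 91.8%, so the plan's overall figures treat the endpoints as independent.

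**2. Validity.** In 20,000 simulated trials at true GMR 0.5 (SD 1.5), the one-sided error of the unadjusted test was 0.0135, 0.0115 and 0.0126 at r = 0, 0.5 and 0.7. For ANCOVA it was 0.0136, 0.0119 and 0.0126. The nominal value is 0.0125. Both methods hold their level.

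**3. Adjusted analysis.** Two-group ANCOVA: replace SD by SD × √(1 − r²) and use df = 2n − 3 = 267. For BA.4/BA.5 at r = 0.3: 1.5 × 0.954 = 1.431; noncentrality 0.693 / (1.431 × 0.1217) = 3.98; power 95.7%. The smallest passing observed BA.4/BA.5 GMR is 0.5 × exp(t × SD × √(1 − r²) × √(2/135)), with t the 0.9875 quantile.

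| r | BA.4/BA.5 power | All 8 | First 4 | All 8 if every GMR is 0.9 | Smallest passing GMR, BA.4/BA.5 |
|---|---|---|---|---|---|
| unadjusted | 93.8% | 90.3% | 91.9% | 66.7% | 0.755 |
| 0.1 | 94.0% | 90.8% | 92.2% | 67.6% | 0.753 |
| 0.2 | 94.7% | 92.0% | 93.2% | 70.6% | 0.748 |
| 0.3 | 95.7% | 93.8% | 94.6% | 75.3% | 0.740 |
| 0.5 | 98.3% | 97.9% | 98.0% | 88.3% | 0.714 |

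The GMR 0.9 column is a further assumption that departs from the plan's GMR of 1.

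**4. Dependence between endpoints.** The same participants supply several endpoints. Under strong positive correlation, all-8 power approaches that of the weakest endpoint. The gain at r = 0.3 is then nearer 95.7 − 93.8 = 1.9 points than 93.8 − 90.3 = 3.5 points.

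**5. Missing baselines.** The evaluable set (SAP 4) does not require a baseline result, and SAP 5.3.2 bars imputation, so the ANCOVA would be complete-case. All-8 power at GMR 1.0, to compare with 90.3% unadjusted at n = 135:

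| Missing baselines | r = 0.1 | r = 0.2 | r = 0.3 |
|---|---|---|---|
| 2% (n = 132) | 89.8% | 91.1% | 93.1% |
| 5% (n = 128) | 88.3% | 89.8% | 92.0% |

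Complete-case ANCOVA is thus a small loss at r = 0.1 with 2% missing, and at r = 0.2 with 5% missing.

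**6. Two-group or pooled model.** The pooled models of SAP 6.3.5.2 have df 5 × 135 − 6 = 669, or 3 × 135 − 4 = 401 for HAI. All-8 power becomes 91.0, 92.2, 94.0 and 98.0% at r = 0.1, 0.2, 0.3 and 0.5. Pooling adds at most 0.2 point over the two-group model, and it brings Groups 6 and 7, from the other enrollment stratum, into the primary model.

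**7. Confidence level.** A 97.5% interval is 2.254 / 1.969 = 1.145 times as wide on the log scale as a 95% interval. With SD 1.5 and r = 0.3, an adjusted GMR between 0.705 and 0.740 has a 95% lower bound above 0.5 but a 97.5% lower bound below it.

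**The case against.** The strongest reply is that this is a preference and not a fault. Protocol and SAP specify the same unadjusted test, and the sample size was computed for exactly that test. The ANCOVA is prespecified for all three assay families, so the effect of baseline adjustment will be visible. SAP 6.3.5.2 shows the unadjusted and the adjusted GMRs side by side at 95%, which is already a like-for-like sensitivity comparison. A reader can recover the 97.5% bound with the factor 1.145. The benefit rests on an undocumented r, and with a few missing baselines even its sign can change.

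Most of this stands. It rules out calling the plan wrong, and it means that changing only the adjusted intervals in 6.3.5.2 to 97.5% would set mismatched levels next to each other. It does not remove the point that the deciding analysis ignores a covariate the trial collects and has already modelled, or that neither interval in 6.3.5.2 can be read directly against the decision rule.

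A reader might infer that the unadjusted test is invalid or the trial underpowered. Steps 1 and 2 show otherwise for the primary contrasts. A reader might also infer that the 95% adjusted interval could be used to claim success. The success rules in Protocol 10.11.11.3.2 and 10.11.11.3.3 rest only on the 97.5% interval.

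**Conclusion.** The point holds as an efficiency weakness. The primary analysis is valid, agrees between the two documents and delivers the stated power. Under the plan's GMR of 1.0 and independent endpoints, adjustment would add about half a point of all-8 power at r = 0.1, 3.5 points at r = 0.3 and 7.6 points at r = 0.5. The gain is smaller if endpoints are strongly correlated and larger if true GMRs lie below 1. It is negligible at r = 0.1 and worth having from about r = 0.3. All of this is conditional on an assumed r.

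One limit applies to the secondary objectives. The primary contrasts lie wholly within stratum 1 (Groups 1 to 5). The secondary contrasts set Groups 6 and 7 (stratum 2) against Groups 3 to 5 (stratum 1). Their validity, adjusted or not, also depends on how participants are allocated between strata, which the text does not state.

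**What to change.** **If it can be documented before the 1-month unblinding:** make the SAP 5.2.2.5 ANCOVA the main analysis for the primary and secondary GMRs, as a two-group model for each contrast with 97.5% CIs, and keep the unadjusted GMR as supportive. Keep participants with a missing baseline in the evaluable set by filling the covariate with the overall mean, written as an explicit exception to SAP 5.3.2. Baseline values below the LLOQ already have a rule there. The cost is a SAP change and a protocol amendment to 10.11.11.3.2 and 10.11.11.3.3, because Protocol 10.11.11 and SAP 2 require one for a major change to the primary analysis, together with a dated record that it preceded unblinding.

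**If it is too late:** in SAP 6.3.5.2, present both the unadjusted GMRs and the LS GMRs with 97.5% CIs, in addition to or in place of the 95% CIs. The two are then comparable with each other and with the 0.5 rule. This is a small wording change and needs no new data. The unblinding date is not in the documents, and Protocol 2.1 already writes of the Substudy A formulation in the past tense, so this may be the only option left.

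In either case, state how participants are allocated between the two enrollment strata.
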